6.0 STUDY MEDICATIONS

6.1 **Lirilumab (Anti-KIR)**

For details regarding dose-calculation of lirilumab, preparation and dispensing of lirilumab, administration of lirilumab, patient monitoring during infusion and treatment of lirilumab related infusion reactions please see the dosing procedure manual (Appendix I).

6.2 **Azacytidine:**

5-azacytidine is commercially available. Commercial supply will be used for purposes of this study. Standard procedures should be used for preparation and administration of 5-azacytidine. The following guidelines are suggested:

Vidaza® (5-azacytidine) (is a cytotoxic drug and, as with other potentially toxic compounds, caution should be exercised when handling and preparing Vidaza® (5-azacytidine) suspensions.

If reconstituted Vidaza® (5-azacytidine) comes into contact with the skin, immediately and thoroughly wash with soap and water. If it comes into contact with mucous membranes, flush thoroughly with water.

The Vidaza® (5-azacytidine) vial is single-use and does not contain any preservatives. Unused portions of each vial should be discarded properly. Do not save any unused portions for later administration.

6.2.1 Preparation for Subcutaneous Administration: Vidaza® (5-azacytidine) should be reconstituted aseptically with 4 mL sterile water for injection. The diluent should be injected slowly into the vial. Vigorously shake or roll the vial until a uniform suspension is achieved. The suspension will be cloudy. The resulting suspension will contain 5-azacytidine 25 mg/mL.

6.2.1.1 Preparation for Immediate Subcutaneous Administration: Doses greater than 4 mL should be divided equally into 2 syringes. The product may be held at room temperature for up to 1 hour, but must be administered within 1 hour after reconstitution.

6.2.1.2 Preparation for Delayed Subcutaneous Administration: The reconstituted product may be kept in the vial or drawn into a syringe. Doses greater than 4 mL should be divided equally into 2 syringes. The product must be refrigerated immediately, and may be held under refrigerated conditions (2°C–8°C, 36°F–46°F) for up to 8 hours. After removal from refrigerated conditions, the suspension may be allowed to equilibrate to room temperature for up to 30 minutes prior to administration.

6.2.1.3 Subcutaneous Administration: To provide a homogeneous suspension, the contents of the syringe must be re-suspended by inverting the syringe 2–3 times and vigorously rolling the syringe between the palms for approximately 30 seconds immediately prior to administration. Vidaza® (5-azacytidine) suspension is administered subcutaneously. Doses greater than 4 mL should be divided equally into 2 syringes and injected into 2 separate sites. Rotate sites for each injection (thigh, abdomen, or upper arm). New injections should be given at least 1 inch from an old site and never into areas where the site is tender, bruised, red, or hard.

6.2.1.4 Suspension Stability: 5-azacytidine reconstituted for subcutaneous administration may be stored for up to 1 hour at 25°C (77°F) or for up to 8 hours between 2°C and 8°C (36°F and 46°F).

6.2.2 Preparation for Intravenous Administration: Reconstitute the appropriate number of Vidaza® (5-azacytidine) vials to achieve the desired dose. Reconstitute each vial with 10 mL sterile water for injection. Vigorously shake or roll the vial until all solids are dissolved. The resulting solution will contain 5-azacytidine 10mg/mL. The solution should be clear. Parenteral drug product should be inspected visually for particulate matter and discoloration prior to administration, whenever solution and container permit.

Withdraw the required amount of Vidaza® (5-azacytidine) solution to deliver the desired dose and inject into a 50-100 mL infusion bag of either 0.9% Sodium Chloride Injection or Lactated Ringer's Injection.

6.2.2.1 Intravenous Solution Incompatibility: Vidaza® (5-azacytidine) is incompatible with 5% Dextrose solutions, Hespan, or solutions that contain bicarbonate. These solutions have the potential to increase the rate of degradation of Vidaza® (5-azacytidine) and should therefore be avoided.

6.2.2.2 Intravenous Administration: Vidaza® (5-azacytidine) solution is administered intravenously. Administer the total dose over a period of 10-40 minutes. The administration must be completed within 1 hour of reconstitution of the VIDAZA vial.

6.2.2.3 Solution Stability: Vidaza® (5-azacytidine) reconstituted for intravenous administration may be stored at 25°C (77°F), but administration must be completed within 1 hour of reconstitution.

6.2.3 Storage: Store unreconstituted vials at 25° C (77° F); excursions permitted to 15°-30° C (59°-86° F) (See USP Controlled Room Temperature). There is no need to protect 5-azacytidine from exposure to light.

6.2.4 Handling and Disposal: Procedures for proper handling and disposal of anticancer drugs should be applied.

6.3 Variations in infusion times of lirilumab or 5-azacytidine due to minor differences in IV bag overfill/underfill and institutional procedure on flushing chemotherapy lines will not result in protocol deviation. All infusion times are considered approximate.

7.0 PATIENT EVALUATION

Every effort will be made to adhere to the schedule of events and all protocol requirements. Variations in schedule of events and other protocol requirements that do not affect the rights and safety of the patient will not be considered as deviations. Such variations may include laboratory assessments completed outside of schedule, occasional missed required research samples such correlative assays.

7.1 Pre-Treatment Evaluation

All pretreatment studies should be obtained within 14 days of entry into the trial, unless otherwise stated.

7.1.1 A complete history and physical, documentation of all measurable disease, concomitant medications and performance status.

7.1.2 CBC, platelet count, differential (differential can be omitted if WBC is $\leq 0.5 \times 10^9/L$).

7.1.3 Creatinine, total bilirubin, ALT or AST.

- 7.1.4 Pregnancy test (urine or plasma) in females of childbearing potential should be performed within 72 hours before initiation of study.
- 7.1.5 Bone marrow aspirate during the last 28 days preceding study initiation. Cytogenetics will be obtained prior to therapy (results from prior analysis can be used for this purpose).
- 7.1.6 Pretreatment optional correlative studies (see below)

7.2 Evaluation During Treatment

- 7.2.1 Physical exam at the start of each cycle (\pm 4 days) and documentation of all concomitant medications.
- 7.2.2 CBC, platelet count, differential once weekly (\pm 4 days) for the first 3 cycles, then every 2-4 weeks (differential can be omitted if WBC is $\leq 0.5 \times 10^9/L$)
- 7.2.3 Creatinine, total bilirubin, ALT once weekly (\pm 4 days) for the first 3 cycles, then every 2-4 weeks.
- 7.2.4 Bone marrow aspiration on day 28 (\pm 7 days), then every 1-3 cycles. Bone marrow tests can be ordered more frequently if mandated by development of peripheral blood counts. No repeat bone marrow is necessary if nonresponse or progressive disease can be unequivocally diagnosed from peripheral blood tests or, in patients with a WBC < 0.3 if the bone marrow test is considered noncontributory by the investigator at any time point.
- 7.2.5 Concomitant medication data will not be collected or entered into the case report form except for concomitant hydroxyurea and cytarabine; however, the subject's medication record will contain a list of concomitant medications.
- 7.2.6 Correlative Studies relating to immunologic response: Tumor tissue, blood samples and bone marrow aspirate will be collected on a separate IRB approved laboratory protocol for immune monitoring as previously published[52-55], under the supervision of the Immunotherapy Platform (MDACC Protocol PA13-0291). Patients will be consented separately on the IRB approved consent for protocol PA 13-0291. Patients may participate in protocol 2014-0862 irrespective of whether they choose to participate on protocol PA 13-0291. In tumor tissues, immunohistochemical studies will be performed to evaluate tumor and immunological cell markers such as CD4 and CD8 T cells. In peripheral blood, we will also evaluate tumor and immune cell populations including but not limited to CD4 and CD8 T cells in pre and post therapy samples.
- 7.2.7

Peripheral blood up to 20 mL (within 24 hours) will be collected under an IRB-approved laboratory protocol for testing of biomarkers at the following time points

- Baseline (prior to 5-azacytidine dose), on day 8 (prior to lirilumab dose), and between days 21 to 28 on cycle 1 (done at MD Anderson).
- In each subsequent cycle blood samples will be obtained on day 1 (prior to 5-azacytidine dose) and day 8 (prior to lirilumab dose) when possible.
- Samples will be collected at progression whenever possible.

Bone Marrow:

- Bone marrow samples will be collected under an IRB-approved laboratory protocol for testing of biomarkers at baseline, at day 28 (+/-7 days), then every 1-3 cycles, and at progression whenever possible.

All these samples can be obtained +/- 3 days. Missed samples for correlative studies will not constitute protocol deviations. All correlative samples are optional.

- 7.2.8 For patients that remain on study with no significant toxicity for more than 6 months, subsequent evaluations during study may be modified after discussion with the principal investigator. These include a decrease in frequency of bone marrow aspirations to every 6-12 months (or as clinically indicated), correlative studies to every 6-12 months (or suspension of sample collection for correlative studies), other laboratory tests to once every cycle.
- 7.2.9 ALL treatments with lirilumab must be administered at the MDACC outpatient clinic. The first cycles of azacytidine must be administered at the MDACC outpatient clinic. Subsequently, patients will have the option of receiving 5-azacytidine injections or infusions at the MDACC outpatient clinic or local ambulatory treatment center. If the local treatment center cannot accommodate 7 consecutive day administration on Days 1-7 of 5-azacytidine, it is allowable to be administered on a 5+2 (days off) + 2 schedule (For example, Administer Monday through Friday, omit Saturday and Sunday, Resume/Administer Monday and Tuesday). In the event that the 5+2+2 schedule is utilized, the Lirilumab will be administered on Day 10, which is allowable by schedule window or +/- 2 days from Day 8. We do not intend for the subjects to receive lirilumab at an outside physician's office. During the first cycle all the laboratory evaluations will be done at MDACC. Subsequently, the patient may have the laboratory work done at a local clinic and the results reported to the research nurse for the study. The laboratory work done at the local clinic will be forwarded to the patient's attending physician at MDACC or PI of the study, who will sign off on the labs to verify that the results have been reviewed.

Outside Physician Participation During Treatment

1. MDACC Physician communication with the outside physician is required prior to the patient returning to the local physician.
This will be documented in the patient record
 2. A letter to the local physician outlining the patient's participation in a clinical trial will request local physician agreement to supervise the patient's care (Appendix H)
 3. Protocol required evaluations outside MDACC will be documented by telephone, fax or e-mail. Fax and/or e-mail will be dated and signed by the MDACC physician, indicating that they have reviewed it. Changes in drug dose and/or schedule must be discussed with and approved by the MDACC physician investigator, or their representative prior to initiation, and will be documented in the patient record.
 4. A copy of the informed consent, protocol abstract, treatment schema and evaluation during treatment will be provided to the local physician.
 5. Documentation to be provided by the local physician will include progress notes, reports of protocol required laboratory and diagnostic studies and documentation of any hospitalizations.
 6. The home physician will be requested to report to the MDACC physician investigator all life threatening events within 24 hours of documented occurrence.
 7. All follow-up visits will be performed at MDACC. Patients will return to MDACC for physical examination at the start of each cycle i.e. approximately every 28 days (+/-7).
- 7.2.10 End of Treatment Visit to be completed 30 days (+/-7 days) after the last dose of study drug. Blood (about 2-3 teaspoons) will be drawn for CBC, platelet count, differential, creatinine, total bilirubin, ALT. No other procedures or labs will be needed.
- 7.2.11 Patients with an objective response at completion of active study treatment will be followed for survival at MD Anderson Cancer Center (MDACC) for up to 90 days after completion of active treatment and while still on study. If the patient is unable to return to MDACC the follow-up visits may be conducted via telephone.

Data regarding adverse events will be collected during the study. Please see **Appendix D** regarding data capturing of adverse events and adverse events source documentation. Protocol specific data will be entered into PDMS/CORE. PDMS/CORE will be used as the electronic case report form for this protocol. Only unexpected AEs will be recorded in the Case Report Form (CRF). The Principal Investigator will sign and date the AE log per each

patient at the completion of each course. Following signature, the AE log will be used as source documentation for the adverse events for attribution.

Treatment may be discontinued for a variety of reasons, including patient withdrawal, investigator decision, and reasons specified by the protocol. Reasons for discontinuation of treatments are described below.

7 CRITERIA FOR RESPONSE:

Response Criteria for AML

Response criteria will be modified from the International Working Group for AML (JCO 2003; 21: 4642-9)[56]. Responders are patients who obtain a CR, CRi, or PR, with or without cytogenetic response, hematologic improvements, and morphologic leukemia-free state. Briefly, criteria are as follows:

8.1.1 Complete remission (CR):

- ◆ Peripheral blood counts:
No circulating blasts
Neutrophil count $\geq 1.0 \times 10^9/L$
Platelet count $\geq 100 \times 10^9/L$
- ◆ Bone marrow aspirate and biopsy:
 $\leq 5\%$ blasts
No Auer rods
No extramedullary leukemia

8.1.2 Complete Remission with Incomplete Platelet Recovery (CRp):

For patients to be classified as being in CRp, they must achieve CR except for incomplete platelet recovery ($< 100 \times 10^9/L$).

8.1.3 Complete remission with incomplete blood count recovery (CRi):

- ◆ **Peripheral blood counts:**
No circulating blasts
Neutrophil count $< 1.0 \times 10^9/L$, or
Platelet count $< 100 \times 10^9/L$
- ◆ **Bone marrow aspirate and biopsy:**
 $\leq 5\%$ blasts
No Auer rods
No extramedullary leukemia

8.1.4 Partial remission:

- ◆ All CR criteria if abnormal before treatment except:
- ◆ $\geq 50\%$ reduction in bone marrow blast but still $> 5\%$

8.1.5 Morphologic leukemia-free state:

- ◆ Bone marrow: $\leq 5\%$ myeloblasts

8.1.6 Hematologic Improvement (HI): Hematologic response must be described by the number of positively affected cell lines.

- ◆ **Erythroid response (E)** (pretreatment Hgb < 11 g/dL)
Hgb increase by ≥ 1.5 g/dL
- ◆ **Platelet response (P)** (pretreatment platelets $< 100 \times 10^9/L$)
Absolute increase of $\geq 30 \times 10^9/L$ for patients starting with $> 20 \times 10^9/L$ platelets
Increase from $< 20 \times 10^9/L$ to $> 20 \times 10^9/L$ and by at least 100%
- ◆ **Neutrophil response (N)** (pretreatment ANC $< 1.0 \times 10^9/L$)
At least 100% increase and an absolute increase $> 0.5 \times 10^9/L$
- ◆ **Blast response (B)**
 $\geq 50\%$ reduction in peripheral blood or bone marrow blasts but still $> 5\%$

9 DISCONTINUATION OF TREATMENT:

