5.2.1.1 The starting dose will be dose level -1.

Table 1. Dose levels of 5-azacytidine and lirilumab during the lead-in phase (part a)

Dose level	5-azacytidine (mg/m ² /d, Days 1-7)	Lirilumab (mg/kg, day 8)
-4	25	0.3
-3	50	0.3
-2	75	0.3
-1	75	1.0 (Starting dose)
0	75	3.0

5.2.1.2 The goal of the lead-in phase is to identify the dose at which <2/6 patients experience DLT. During the lead-in phase the dose’s of 5-azacytidine and lirilumab may be reduced if 2 or more patients experience DLT at any given dose. After the lead in phase the dose of lirilumab may not be reduced in the phase II portion of the study. For potential lirilumab related AEs in the phase II portion of the study only dose interruptions of lirilumab will be permitted. Dose reductions or escalations of 5-azacytidine will continue to be permitted in the phase II portion of the study and dose reductions or escalations of 5-azacytidine beyond those mentioned in table 5 or different to the doses specified should be discussed with the PI and documentation of the justification recorded in the chart.

5.2.1.3 The dose and /or schedule of administration is subject to modification pending information from ongoing clinical trials of lirilumab as a single agent and in combination with other drugs.

DLT is defined as clinically significant non-hematologic adverse event or abnormal laboratory value assessed as unrelated to disease progression, intercurrent illness, or concomitant medications and occurring during the first cycle on study that meets any of the following criteria:

- CTCAE Grade 3 AST (SGOT) or ALT (SGPT) for ≥ 7 days
- CTCAE Grade 4 AST (SGOT) or ALT (SGPT) of any duration
- All other clinically significant non-hematological adverse event that is Grade 3 or 4 according to the NCI common terminology criteria version 4.0 with the following exceptions:
 - Grade 3 or 4 nausea, vomiting and diarrhea will be considered DLT only if not controlled by optimal therapy.
 - Grade 3 biochemical abnormalities (e.g., lipase or bilirubin elevation) will only be considered DLT if accompanied by clinical consequences. Grade 3 or 4 electrolyte abnormalities will only be considered DLT if possibly related to study drug and not corrected by optimal replacement therapy.

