5.2.1.4 We will first treat 6 patients at dose level -1 in the lead-in phase. If DLT occurs in $\geq 2/6$ patients, this dose level would exceed the MTD, and 6 patients will be treated at the next lower dose level (i.e. dose level -2). If DLT is observed in the first 28 days of treatment in 0 or 1/6 at dose level -1, then dose level 0 will be evaluated. The dose adjustment (Table 1) will continue in cohorts of 6 until we reach a dose level at which $< 2/6$ patients experience a DLT in the first 28 days. The dose level at which 0-1/6 patients experience a DLT in the first 28 days of treatment will be the MTD and will be used to treat an additional 34 patients in the phase II portion of the study. If $\geq 2/6$ patients experience DLT at dose level -4, the study will be revised to consider additional lower dose levels (based on potential synergistic toxicity).

5.2.1.5 Patients that are removed from study before day 28 for any reason other than toxicity and have not experienced DLT will be replaced.

5.2.2 One cycle of therapy is defined as 28 days. Patients will receive one cycle of therapy every 28 days (+/- 7 days).

5.2.2.1 In the phase II part of the study (once the MTD dose has been defined) cycles may be started early (but not earlier than day 21) for patients with active disease if judged in the best interest of the patient.

For the lead-in cohort, DLT defining period is 28 days. As such, cycle 2 should not be started before 28 days for the patients being treated on the lead-in cohort.

5.2.2.2 Subsequent cycles may be delayed for recovery of toxicity or other medical conditions (e.g. infections). Delays in start of subsequent cycles greater than 8 weeks will be acceptable only for patients who are deriving clinical benefit and after discussion with the principal investigator of potential risk/benefit ratio.

5.2.2.3 In instances where one drug has to be discontinued transiently because of safety, the administration of the other drug may continue as scheduled. If the drug that is held can resume at a later time, no doses will be made up and the administration will follow the originally defined schedule calendar according to the drug that was continued.

5.2.2.4 Subsequent courses of 5-azacytidine and lirilumab may be administered regardless of peripheral blood counts during the first 4 cycles and/or in the presence of residual leukemia.

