 - Grade 2 fatigue or laboratory abnormalities do not require delay, however
 - ◆ For a subject with baseline AST, ALT, or total bilirubin within normal limits, delay dosing for drug-related Grade ≥2 values
- Any Grade 3 skin AE, or Grade 3 laboratory abnormality, with the following exceptions:

- Grade 3 lymphopenia or leukopenia does not require dose delay.
- If a subject has Grade 1 baseline AST, ALT, or total bilirubin, delay dosing for drug-related Grade 3 toxicity
 - Any AE, laboratory abnormality, or intercurrent illness, which in the judgment of the investigator, warrants delaying the dose of study medication.
 - Lirilumab dose reductions are not permitted in this study (only dose delays when indicated).

Subjects may resume treatment with study drug when the drug-related AE(s) resolve to Grade ≤ 1 or baseline value, with the following exceptions:

- Subjects may resume treatment in the presence of Grade 2 fatigue
- Subjects who have not experienced a Grade 3 drug-related skin AE may resume treatment in the presence of Grade 2 skin toxicity
- Subjects with baseline Grade 1 AST/ALT or total bilirubin who require dose delays for reasons other than a 2-grade shift in AST/ALT or total bilirubin may resume treatment in the presence of Grade 2 AST/ALT OR total bilirubin
- Subjects with combined Grade 2 AST/ALT AND total bilirubin values meeting discontinuation parameters (Discontinuation Section below) should have treatment permanently discontinued
- Drug-related pulmonary toxicity, diarrhea, or colitis, must have resolved to baseline before treatment is resumed
- Drug-related endocrinopathies adequately controlled with only physiologic hormone replacement may resume treatment

If the criteria to resume treatment are met, the subject should restart treatment at the same dose at the next scheduled timepoint per protocol. The next scheduled time point for 5-azacytidine is the projected day 1 of the next cycle. The next scheduled time point for Lirilumab is the projected day 8 of the next cycle. These will be the next scheduled time points irrespective of the patients current dose level. However, if the treatment is delayed past the next scheduled timepoint per protocol, the next scheduled timepoint will be delayed until dosing resumes. Patients who receive combination therapy in whom continuation of 5-azacytidine is considered to be inadequate, or inappropriate (e.g., because of pancytopenia) can discontinue 5-azacytidine and continue with lirilumab only.

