5.3.4 Lirilumab Discontinuation Criteria

Treatment should be permanently discontinued for the following:

- Any Grade 2 drug-related uveitis or eye pain or blurred vision that does not respond to topical therapy and does not improve to Grade 1 severity within the re-treatment period OR lasting > 7 days with systemic treatment
- Any Grade 3 non-skin, drug-related adverse event lasting > 7 days, with the following exceptions for drug-related laboratory abnormalities, uveitis,

pneumonitis, bronchospasm, diarrhea, colitis, neurologic adverse event, hypersensitivity reactions, and infusion reactions:

- Grade 3 drug-related uveitis, pneumonitis, bronchospasm, diarrhea, colitis, neurologic adverse event, hypersensitivity reaction, or infusion reaction of any duration requires discontinuation
- Grade 3 drug-related laboratory abnormalities do not require treatment discontinuation except those noted below:
- Any drug-related liver function test (LFT) abnormality that meets the following criteria require discontinuation: AST or ALT > 8 x ULN
- Any Grade 4 drug-related adverse event or laboratory abnormality, except for the following events which do not require discontinuation:
 - Isolated Grade 4 amylase or lipase abnormalities that are not associated with symptoms or clinical manifestations of pancreatitis and decrease to < Grade 4 within 1 week of onset.
 - Isolated Grade 4 electrolyte imbalances/abnormalities that are not associated with clinical sequelae and are corrected with supplementation/appropriate management within 72 hours of their onset
- Any dosing interruption lasting > 8 weeks with the following exceptions:
 - Dosing interruptions to allow for prolonged steroid tapers to manage drug-related adverse events are allowed. Prior to re-initiating treatment in a subject with a dosing interruption lasting > 8 weeks the Investigator must be consulted. Tumor/Leukemia assessments should continue as per protocol even if dosing is interrupted.
 - Dosing interruptions > 8 weeks that occur for non-drug-related reasons may be allowed if approved by the Investigator. Prior to re-initiating treatment in a subject with a dosing interruption lasting > 8 weeks the Investigator must be consulted. Tumor/Leukemia assessments should continue as per protocol even if dosing is interrupted.

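### AST is a separate trigger in the DLT, lirilumab delay and lirilumab stopping rules, but no scheduled visit requires it, so an AST-only event cannot be found from the required tests

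*Combined protocol and SAP*

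**What the plan says.** **Rules that read AST**

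- Section 5.2.1.3 (DLT definition, first cycle): "CTCAE Grade 3 AST (SGOT) or ALT (SGPT) for" at least 7 days, and separately "CTCAE Grade 4 AST (SGOT) or ALT (SGPT) of any duration".
- Section 5.3.3 (lirilumab delay): "For a subject with baseline AST, ALT, or total bilirubin within normal limits, delay dosing for drug-related Grade" 2 or higher. A parallel rule delays at Grade 3 when the baseline value was Grade 1.
- Section 5.3.4 (lirilumab discontinuation): "AST or ALT > 8 x ULN", if drug-related.

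**Tests that are required**

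- Section 7.1.3 (baseline): "Creatinine, total bilirubin, ALT or AST".
- Section 7.2.3 (on treatment): "Creatinine, total bilirubin, ALT once weekly", with a window of 4 days either way, for three cycles, then every 2-4 weeks.
- Section 7.2.10 (End of Treatment Visit): "total bilirubin, ALT. No other procedures or labs will be needed".
- Section 9.1.4 (discontinuation or early withdrawal): a short chemistry panel with either transaminase.

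**Decision that uses the DLT count**

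Section 5.2.1.4: "The dose level at which 0-1/6 patients experience a DLT in the first 28 days of treatment will be the MTD". That level is then given to 34 further patients. Two or more DLTs in six fail the level.

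**The concern.** A toxicity criterion can only count what is measured. Here three safety rules depend on an analyte that the visit schedule never makes mandatory, and that is absent from scheduled on-treatment chemistry altogether. Liver toxicity is not remote for this regimen: Section 5.3.7.4 gives autoimmune hepatitis as an example of an event likely to be due to lirilumab.

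The lead-in decision is sensitive to a single patient. At dose level -1, a wrongly passed cohort leads to six patients being treated at the higher lirilumab dose. At the level finally chosen, it leads into phase II. The medical monitor's cohort review (Section 5.2) does not close the gap, because it can use only values that exist. In phase II the same gap affects the AST arms of the delay and stopping rules.

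A lesser question is whether the scheduled draws can settle if a Grade 3 transaminase lasted 7 days, which is what separates a DLT from a non-DLT at that grade.

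**Working it through.** The plan states no figure on this point, so there is none to reproduce. The check is a comparison of rules and tests, followed by short arithmetic.

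**1. Rule against schedule**

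| Time point | Section | ALT required? | AST required? |
|---|---|---|---|
| Baseline | 7.1.3 | Either enzyme suffices | Either enzyme suffices |
| On treatment | 7.2.3 | Yes | No |
| End of Treatment Visit | 7.2.10 | Yes | No |
| Discontinuation | 9.1.4 | Either enzyme suffices | Either enzyme suffices |

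Scheduled on-treatment AST results: 0. From required tests alone, no AST-only event is found under Sections 5.2.1.3, 5.3.3 or 5.3.4. This needs no assumption about event rates.

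**2. Effect on the lead-in count**

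Take a cohort with two patients with DLT, one of them AST-only. The true count is 2/6 (fail); the count from required tests is 1/6 (pass).

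For illustration only, let q be the probability that a patient has a DLT that is seen. A level passes with probability

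P(pass) = (1 − q)^6 + 6q(1 − q)^5.

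Assume a true DLT rate of 30%, and that AST-only DLTs in patients with no other DLT make up 0, 5 or 10 percentage points of it, all missed:

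- q = 0.30: 0.118 + 0.303 = 0.420
- q = 0.25: 0.178 + 0.356 = 0.534
- q = 0.20: 0.262 + 0.393 = 0.655

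The 30%, 5 and 10 are assumed. The documents give no AST-only rate, so these figures show only how sensitive the rule is.

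**3. Spacing of draws**

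Weekly draws, each movable by 4 days, can be 7 + 4 + 4 = 15 days apart. One Grade 3 value between two lower values is consistent with any duration up to just under 14 days with exact weekly draws, or just under 14 + 4 + 4 = 22 days at the window limits. Such a pattern cannot by itself be placed above or below 7 days.

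**4. Dependence on the counting rule**

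Consider exact weekly draws, onset uniform over the week, Grade 3 throughout the episode, and no unscheduled tests. Two conventions are plausible.

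- *Convention A: two Grade 3 values at least 7 days apart.* An 8-day episode qualifies only if it spans two draws: (8 − 7)/7 = 14%.
- *Convention B: from the first Grade 3 value to the first lower value.* An 8-day episode always contains a draw, and the first lower draw is at least 7 days after the first Grade 3 one: 100%. A 3-day episode also counts whenever a draw falls inside it: 3/7 = 43%.

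Letting draws move by independent uniform whole-day offsets (simulation, 400,000 courses per setting), an 8-day episode is classed as 7 days or more as follows:

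| Window used | Convention A | Convention B |
|---|---|---|
| Exact weekly | 14% | 100% |
| 1 day either way | 5% | 74% |
| 4 days either way | 2% | 67% |

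The convention moves the answer far more than the window does, and the plan specifies neither convention.

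**The case against.** **On AST.** The strongest reply is that the two enzymes are treated as interchangeable. Eligibility (Section 4.1.7), baseline and discontinuation all use an either/or wording, and AST may come with a routine panel. Harm also needs a chain of events: a qualifying AST rise without a qualifying ALT rise, in a patient with no other DLT, in a cohort whose true count is exactly two. This limits the likely impact and stands as a reason not to overstate it. It does not remove the mismatch, because Section 5.2.1.3 lets AST alone make a DLT and no passage requires the test. Appendix G may advise more liver tests, but its text is not shown and Section 5.3.5 calls it guidance.

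**On duration.** Weekly ALT in cycles 1-3 is itself a scheduled retest. Table 2 in Section 5.3.2 requires both drugs to be held for clinically significant drug-related Grade 3 or 4 events and separates recovery within 14 days from persistence for 15-28 days, which cannot be applied without repeat values. So a reader should not infer that Grade 3 values go unrepeated, or that most episodes longer than 7 days would be missed. The second inference holds only under Convention A with no unscheduled tests. Under Convention B the error also runs towards over-calling short episodes, which is conservative for dose selection.

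**Two further inferences have little force.** A patient with only AST at baseline might seem to lack a reference value for the ALT delay rule. But lirilumab is first given on Day 8 (2 days either way), and if weekly draws begin at Day 1, an ALT would precede it. It may also seem that DLT duration is lost because Section 10.3 puts only a per-course extreme on the case report form. Adverse events are also documented in the medical record and a signed log, and a cohort summary is reviewed, so the form need not be the source for DLT calls.

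**Conclusion.** The AST mismatch holds on the text alone. Three safety rules use AST as an independent trigger, no visit makes it mandatory, and no on-treatment draw includes it. A site in full compliance cannot detect an AST-only DLT, delay or stop from required tests, and one missed DLT can reverse a lead-in decision at 2/6.

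A reader might infer that the MTD will therefore be set too high. The documents do not support that: they give no frequency for AST-only events, routine panels or unscheduled tests may supply the values, and the pass probabilities above rest on assumed rates. The effect on the MTD cannot be sized.

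The duration point is secondary. The permitted spacing of up to 15 days does not by itself settle the 7-day criterion, and the result turns on an unstated counting rule. The percentages shown demonstrate that dependence; they are not bounds on the trial's true detection rate. The correction is worth making because it is cheap and bears directly on safety decisions.

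**What to change.** 1. In Sections 7.1.3, 7.2.3 and 7.2.10, require both AST and ALT. Cost: one added analyte on blood already drawn, and nothing further where AST is already reported.
2. In lead-in cycle 1, after any Grade 3 AST or ALT, repeat both within 2-3 days and again at day 7. Cost: one or two extra draws per event, in a cycle when all laboratory work is already done at the study centre (Section 7.2.9).
3. In Section 5.2.1.3, state that the 7 days run from the first Grade 3 value, and say what ends the count (for example, the first lower value).

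The repeats will not resolve every borderline case. Under Convention A with exact weekly draws, the day-7 repeat adds nothing and an 8-day episode stays at 14%. This is why the counting rule needs to be written down as well.
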